1.3 Research questions and hypotheses, theoretical approach and methodology

Main hypothesis: The web-based intervention 5WaysA will improve wellbeing and mastery and hence provide the municipalities with an effective measure for mental health promotion.

Research questions:

1. *To what extent does participation in the web-based 5WaysA intervention lead to improved wellbeing, mental health and mastery in the general population?*
2. *To what extent are the effects short-term and long-term (i.e., 10 weeks and 12 months)?*
3. *What mechanisms explain potential improvements in wellbeing?*
 - a) *For whom is this intervention effective (i.e., is the effect moderated by e.g. gender, age, education)?*
 - b) *What mechanisms (e.g., regular practicing of 5Ways actions, increased social activity or support) explain intervention effects?*

Sample: The sample consists of participants from the general population in Norwegian municipalities. A cooperation with public health alliances in the Viken and Trøndelag regions, as well as Sunne kommuner, the Norwegian WHO Healthy Cities network, has already been established. Public health coordinators in all of the municipalities will be involved in recruitment. Invitations to participate will be distributed via emails, the municipalities' web sites, social media, local newspapers, citizen panels (e.g., *Innbyggerpanelet* in Bærum) and related means. We plan to recruit a minimum of 1500 participants. The participants will be randomized to either an intervention group ($n=750$) or one of two wait-list control groups (active control group, $n=375$) (passive control group, $n=375$), receiving the intervention five months later. Citizen panels, like the one we will recruit from in Bærum, invites inhabitants to contribute with experiences and opinions about their lives in the municipality and about municipal services. The citizens' opinions contribute to new understandings, new ideas, innovative solutions and development. All participating regions and networks involved in our study have a strong tradition for involving the citizens in their work and have implemented wellbeing in their regional strategies.

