Design: The design is a randomized controlled trial (RCT), with one intervention group and two wait-list control groups. The goal with this design is to demonstrate the initial efficacy and feasibility of the 10 week 5WaysA intervention. We choose an RCT with two wait-list control groups, where one wait-list is writing activity log and the other is passive while waiting. We add the active control because we are aware of the limitations in passive wait-list control group conditions. However, both wait-list control groups will know they are waiting for an intervention, which can in turn produce demand characteristics. The intervention group will receive the 5WaysA intervention within a few weeks after announcing their interest in participating in the study. The wait-list control groups will receive the 5WaysA intervention 5 months after the intervention group had the intervention. The active wait-list control group is encouraged to write an activity log every week. The passive wait-list control group is not getting any tasks while they are waiting, other than a questionnaire. Figure 2 shows the time line for recruiting, randomizing and the schedule for intervention and measurement points (M).

Power analysis: We assume that we can recruit a minimum of 1500 participants, but high drop-out is expected. An a priori power analysis was conducted using G*Power3[40] to test the interaction effect in a mixed ANOVA, using a two-tailed test, assuming a small effect size ($f = .10$), and an alpha of .05. The assumed effect size ($f=0.1$) was chosen as it is of the same magnitude (lower bound) as has been reported by other universal interventions with wellbeing as the outcome measure[41]. The result showed that if we attained a total sample of 750 participants at our second measurement point (attrition of 50 %), we would have power of .999 to detect a group by time interaction. The high level of statistical power will enable us to investigate both moderators and mediators.

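### Moderator question 3a has an open list, no exploratory label and no error rule, and the .999 power cited in its support applies only to the overall group-by-time effect

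*Combined protocol and SAP*

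**What the plan says.** Section 1.3 lists three research questions. The third concerns mechanisms, and its part (a) reads: "For whom is this intervention effective (i.e., is the effect moderated by e.g. gender, age, education". Part (b) asks which mechanisms explain the effects. The work plan in section 3.2 schedules mediators and moderators as an analysis task, so these analyses are intended.

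The Power analysis paragraph of section 1.3 sets the calculation up as a mixed-ANOVA interaction test, "using a two-tailed test, assuming a small effect size ($f = .10$), and an alpha of .05". With 750 participants at the second measurement the result is "we would have power of .999 to detect a group by time interaction". The next sentence reads: "The high level of statistical power will enable us to investigate both moderators and mediators".

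The Measurement paragraph makes wellbeing primary and measures it with several instruments, including a 23-question shortlist, the SWLS and the Flourishing Scale. The Data analysis paragraph plans a two-way mixed ANOVA and linear mixed models over all time points. It gives no moderator model, closed list, designated scale or time, significance level, adjustment or exploratory label for questions 3a and 3b. The only alpha in the document is the .05 used in the power calculation.

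**The concern.** Two things are joined that should be kept apart. The .999 describes a test of the average effect. The sentence after it uses that figure to support tests of whether the effect differs between groups of people. Those tests estimate a difference between two effects and are much less precise at the same sample size.

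The moderator family is also undefined. The list is introduced by examples, so others can be added, and no rule says what a nominally significant interaction would entitle the authors to conclude. A chance interaction could then be reported as the answer to a stated research question, from a trial described as highly powered for it. A non-significant one could equally be read as evidence that the effect is the same in everyone, when the test may have had little power. At stake is whether the report may say that the programme is effective for some people and not for others.

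**Working it through.** **Inputs from section 1.3.** f = 0.10; two-tailed alpha .05; N = 750 after 50% attrition from 1500; stated power .999; allocation 750:375:375, which is 1:1 if the two control groups are pooled; three named moderators.

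**Assumptions, since the document does not give them.** Number of measurements m = 2; correlation between measurements ρ = .5; a binary moderator with share p in one category, independent of treatment.

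**1. Reproduce the .999.** For a within-between interaction in the G*Power form:

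λ = f² × N × m / (1 − ρ) = 0.01 × 750 × 2 / 0.5 = 30, with df1 = (k − 1)(m − 1) and df2 = (N − k)(m − 1).

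- k = 2 groups (df 1, 748): power 0.9998.
- k = 3 groups (df 2, 747): power 0.9992.

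The stated figure reproduces. It depends on ρ: at ρ = 0, λ = 15 and power is 0.972 (two groups) or 0.943 (three groups).

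**2. Power for a moderator under the same assumptions, controls pooled.** The variance of a difference between two subgroup effects is that of the overall effect divided by p(1 − p). If the subgroup difference is a fraction c of the assumed overall effect, then:

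λ_mod = 30 × c² × p(1 − p)

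| p | c | λ_mod | Power at .05 | Power at .05/3 = .0167 |
|---|---|---|---|---|
| .5 | 1 | 30 × 1 × .25 = 7.5 | 78% | 63% |
| .5 | 0.5 | 30 × .25 × .25 = 1.875 | 28% | 15% |
| .3 | 1 | 30 × 1 × .21 = 6.3 | 71% | 54% |
| .3 | 0.5 | 30 × .25 × .21 = 1.575 | 24% | 13% |

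With p = .5, c = 1 means that one half of the sample gains 1.5 times the average effect and the other half 0.5 times. c = 0.5 means 1.25 and 0.75 times.

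**3. Chance of a false moderator finding.** Assume no true moderation and each named moderator tested once, unadjusted, at two-sided .05, on one scale at one time.

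- Independent tests: 1 − 0.95³ = 0.143.
- All three statistics correlated .3: 0.136 (simulation from a multivariate normal).
- All three correlated .5: 0.125 (same method).

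Each added moderator raises the figure. With independent tests, four give 1 − 0.95⁴ = 18.5% and five give 1 − 0.95⁵ = 22.6%.

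**4. With adjustment.** At .0167 per test, three independent tests give 1 − (1 − .0167)³ = 4.9%. Holm keeps the family-wise rate at or below 5%.

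**The case against.** The strongest reply is that the plan promises little here. Question 3a is a sub-item of the third question, and the main hypothesis does not mention subgroups. The power sentence says that moderators will be investigated, which commits to no confirmatory conclusion. The design is described as testing initial efficacy and feasibility. Preregistration is promised and could close the list. Moderator analyses are in any case usually read as exploratory.

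Much of this stands, and it limits the point in four ways.

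- A reader might infer that the plan expects its power to settle the moderator question. The wording does not go that far. Nor does any passage set .05 as the threshold for moderators; that threshold is an assumption of the calculation.
- A reader might infer that the false-positive risk is at least 14%. That is not a bound: correlated tests bring it to 12.5–13.6%.
- A reader might cross the moderators with every scale and time and quote far larger figures. Three moderators on three scales at one time, for example, would give about 22–33% under assumed scale correlations of .9 to .5. The document describes no such grid, and in the planned mixed model a moderator could enter as a single term. The risk rises with added moderators, scales or times, by an amount the document does not determine.
- A reader might infer that subgroup results will be used to target the programme. The aim of informing municipal priorities concerns the intervention as a whole.

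The reply fails on two points. The description of the design's goal covers the whole trial and does not label 3a exploratory. And the sentence rests the moderator work on a power figure that does not apply to it, which neither convention nor a promise of preregistration corrects.

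**Conclusion.** The concern holds in a limited form. The .999 is sound for the overall group-by-time effect under plausible inputs, but it does not carry over to moderators: with an even split, power is about 78% in a favourable case and about 28% when the subgroup difference is half the assumed effect. These figures rest on two time points, ρ = .5, pooled controls and 750 analysed. Without adjustment, the three named moderators alone carry roughly a one-in-seven to one-in-eight chance of a false finding, if there is no true moderation and each is read at .05 on one scale at one time.

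This is more than missing detail, because it determines what the trial may conclude about subgroups. It does not affect the test of the overall effect. The documents also do not support the view that family-wise adjustment is obligatory: an exploratory label with interval estimates is an adequate alternative.

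**What to change.** In the protocol or the preregistration:

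1. In question 3a, delete the abbreviation that leaves the list open. Prespecify three interactions: treatment by gender, treatment by age (continuous) and treatment by education. Test them on the primary wellbeing score at the 10-week comparison. This requires that one score be named as primary.
2. Label 3a and 3b exploratory. Report interaction estimates with 95% confidence intervals, and draw no conclusion from an unadjusted test that the programme is effective for a particular subgroup.
3. Replace the sentence on power for moderators and mediators with one saying that both will be explored and that the .999 does not apply to them.
4. Apply Holm over the three interactions only if the sponsor wants a confirmatory subgroup claim. The smallest p-value is then compared with .0167, where power for an evenly split moderator is about 63% (full assumed effect) or 15% (half of it).

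The change is a few sentences and needs no further data. The downside is a weaker claim for the moderator and mediator analyses, and lower power if the Holm option is chosen.

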Lack of research: The OECD report “Understanding effective approaches to promoting mental health and preventing mental illness” from 2017 concluded that there is a sound and quite extensive evidence base for effective and cost effective actions to promote mental wellbeing and prevent mental ill-health[21]. There are, however, few studies on ways to enhance wellbeing in the general population, and especially through web-based universal interventions. A few meta-analyses have been published, showing that face-to-face delivered positive psychological interventions are effective in improving wellbeing, with effect sizes of Cohen’s d in the range of 0.2-0.3. Sin and Lyubomirsky[22] concluded in their meta-analysis that positive psychology interventions significantly enhance wellbeing (mean $r=0.29$) and decrease depressive symptoms (mean $r=0.31$). A later meta-analysis by Bolier et al. in 2013[23] showed that the standardized mean difference was 0.34 for SWB (life satisfaction and positive affect), 0.20 for psychological wellbeing (PWB [optimal functioning in terms of e.g. mastery, hope, purpose in life]) and 0.23 for depression. Both meta-analyses indicate small, but significant effects for positive psychology interventions. A more recent review and meta-analysis, testing multi-component positive psychological interventions in both clinical and non-clinical samples, reported standardized mean effects of 0.34 for SWB, 0.39 for PWB, 0.29 for depression and 0.35 for anxiety and stress, indicating small to moderate effects[24]. Another recent meta-analysis looked at the effects of a wide range of RCT studies on positive psychology intervention targeting non-clinical population. This meta-analysis included both interventions using technology-assisted methods and traditional methods

(face-to-face). Results showed that positive psychology interventions increase wellbeing. The overall effect size was 0.23; 0.08 for PWB, 0.22 for SWB, and 0.43 when the studies targeted both types of well-being. Interventions based on traditional methods were more effective than those that used technology-assisted methods. However, technology-assisted interventions were effective too (0.27). This meta-analysis concludes that it is a lack of empirical studies with a aim to understand the success of wellbeing interventions via technology[25].

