Procedures: The webinar will be a live lecture with an independent trained facilitator. Questionnaires will be administrated and distributed by the project manager using the Nettskjema and Services for sensitive data (TSD) tools. The measurements for the intervention group will be conducted when the participants register to participate (baseline, just before the main webinar) (M1), at the booster session webinar one months after the completed main webinar (M2), 10 weeks after the main webinar (M3), five months after the main webinar (when control groups are starting) (M4) and 12 months after the intervention is completed (M5). Control groups will be measured when the participants register to participate (baseline, just before the main webinar) (M1), when the interventions group has completed the intervention (M2), when they start the intervention (main webinar) (M3), at the booster session one months after the completed main webinar (M4), ten weeks after the main webinar (M5) and 12 months after the intervention is completed (M6)

Data analysis: The effect analysis will involve a comparison of self-reported wellbeing at different measurement points, using a two-way mixed measures ANOVA. In addition, we will run a longitudinal analysis using linear mixed (multilevel) models on the data from all five measurement time points. Mixed modelling is a flexible way to handle unbalanced data in case of non-registration and repeated observations. The models allow us to investigate the effects of the intervention and test the hypotheses of group and individual development in wellbeing while controlling for both stable and time-varying covariates.

Ethics and privacy: All the participants will receive a letter of information about the study, also specifying the requirements of The Regional Committees for Health Research Ethics (REK). A written consent from all participants in all groups will be obtained. All sensitive personal information will be handled according to GDPR requirements. Data will be stored and analyzed under the Services for sensitive data (TSD) at UiO. The study will be preregistered in Open Science Network/Clinicaltrials.gov.

Risks: There is a low probability that this study leads to any disadvantage, damage or risk for the participants. The activities they are encouraged to engage in are universal, general and easy to adapt to differences in age, culture, socioeconomic background and state of health.

| Risk | Consequences | Planned measures |

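### The stated power of .999 is not power for a small effect on its most natural reading, and it does not carry over to the moderator and mediator analyses

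*Combined protocol and SAP*

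**What the plan says.** All references are to the combined protocol and SAP.

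- **Section 1.3, Power analysis.** The calculation used G*Power 3 for the interaction in a mixed ANOVA, "assuming a small effect size ($f = .10$), and an alpha of .05". The effect size is described as the lower bound reported for other universal wellbeing interventions. The result is "a total sample of 750 participants at our second measurement point (attrition of 50 %), we would have power of .999". The paragraph ends: "The high level of statistical power will enable us to investigate both moderators and mediators".
- **Section 1.3, Research questions.** Question 3a asks for whom the intervention works: "is the effect moderated by e.g. gender, age, education".
- **Section 1.3, Data analysis.** The effect analysis compares wellbeing at different measurement points "using a two-way mixed measures ANOVA". A linear mixed model over the five time points is planned in addition. Neither the time points in the ANOVA nor any pooling of the two control groups is fixed.
- **Section 1.3, risk table.** The sample is relied on to give adequate power for small effects as well.
- **Section 1.1, Lack of research.** Face-to-face interventions are summarised as having Cohen's "d in the range of 0.2-0.3", and "technology-assisted interventions were effective too (0.27"). The text also warns that true effects are probably somewhat smaller than published ones.

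The power paragraph does not give the correlation between repeated measurements, the number of groups and measurements entered, or the G*Power effect-size option.

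**The concern.** In a repeated-measures design, f = .10 has no fixed meaning in SD units. It depends on the effect-size option, the number of measurements and, under some options, the correlation. A reader who sees f = .10 called small will take .999 to mean near-certain detection of effects of the size the plan cites. If f = .10 stands for something nearer 0.40 SD, that is not what was shown.

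The second issue holds whichever option was used. Power for an overall group-by-time effect is not power for a difference in that effect between subgroups. Moderation is a listed research question, and the project is meant to inform municipal decisions. A null moderator result from a test with low power could be read as evidence that the intervention works equally well for everyone.

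**Working it through.** **Inputs from the plan:** N = 750 analysed, alpha .05, f = .10, allocation 750:375:375 (2:1:1).

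**Assumptions:** equal attrition (375 intervention, 375 controls in total), the two control groups alike, equal SDs over time, and a correlation r of .5 to .7 (the documents give none).

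**1. Reproducing .999.** Power comes from the noncentral F distribution with k groups and m measurements.

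- Default option: λ = N f² m/(1 − r). With k = 3, m = 2, r = .5: λ = 750 × 0.01 × 2/0.5 = 30, power **.9992**. With r = .3 power is .990, and with r = 0 (λ = 15) it is .943.
- 'As in Cohen' option: λ = N f² (m − 1). With m = 2: λ = 7.5, power **.69** (k = 3) or **.78** (k = 2).

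**2. What f = .10 means on the default two-measurement reading.** With half the sample in intervention and half in control, a net change of D (in SD units) gives interaction effects of ±D/4. So f = D/4 and D = 4 × 0.10 = **0.40 SD**.

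**3. Power at effects the plan cites, two time points.** The interaction test equals a test on change scores, with variance v = 2(1 − r) and λ = D²/[v(1/375 + 1/375)].

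- D = 0.20, r = .5: v = 1, λ = 0.04/0.005333 = 7.5.
- D = 0.20, r = .7: v = 0.6, λ = 0.04/0.0032 = 12.5.
- D = 0.27, r = .5: λ = 0.0729/0.005333 = 13.67; r = .7: λ = 0.0729/0.0032 = 22.78.

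| Net change | r | Three groups (2 df) | Controls pooled (1 df) |
|---|---|---|---|
| 0.20 SD | .5 | .69 | .78 |
| 0.20 SD | .7 | .90 | .94 |
| 0.27 SD | .5 | .92 | .96 |
| 0.27 SD | .7 | .99 | .997 |

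Outside the assumed range of r, three-group power at 0.20 SD is .53 at r = .3 and .98 at r = .8. A simulation of change scores (10,000 runs; groups of 375, 188 and 187) gave .683 and .893 at r = .5 and .7.

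**4. A favourable case for the longitudinal model.** The control schedule reads "when the interventions group has completed the intervention (M2), when they start the intervention (main webinar) (M3"). Controls therefore contribute a baseline and at most two untreated follow-ups. Average those two, adjust for baseline, and assume a sustained effect, equal correlations and no further dropout. Then v = (1 + r)/2 − r².

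- r = .5: v = 0.50, λ = 0.04/(0.50 × 0.005333) = 15, three-group power .94.
- r = .7: v = 0.36, λ = 0.04/(0.36 × 0.005333) = 20.8, three-group power .99.

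**5. Moderators.** For two equal subgroups with controls pooled, the variance of a difference between two subgroup effects is four times that of the overall effect, so λ is divided by 4. For an illustrative subgroup difference of 0.20 SD:

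| Case | r = .5 | r = .7 |
|---|---|---|
| Two time points | λ = 1.875, power .28 | λ = 3.125, power .42 |
| Favourable case | λ = 3.75, power .49 | λ = 5.21, power .63 |

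Reaching 80% power needs a subgroup difference of 0.41 SD (r = .5) or 0.32 SD (r = .7), or 0.29 and 0.25 SD in the favourable case. With an 80/20 split, two-time-point power at 0.20 SD falls to .19-.29.

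Mediation power was not computed, because the documents give no path sizes.

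**The case against.** **The figure is right and fairly robust.** Under the default option with 2-3 groups, 2-5 measurements and r of .3 to .7, power is always about .99 or more. This stands. A reader might infer that .999 is a miscalculation, and the documents do not support that. The difficulty is which effect it refers to.

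**0.40 SD is neither confirmed nor outside the cited effects.** This also stands. The two-measurement default fits the reference to a second measurement point, but the settings are unstated. Section 1.1 lists wellbeing effects up to 0.43, and a mean r of 0.29 that converts to d = 2 × 0.29/√(1 − 0.29²) ≈ 0.61. It also lists 0.08 for psychological wellbeing. So 0.20 SD is a sensitivity value. It is neither the plan's target nor its lowest cited effect.

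**The range of .69-.90 depends on choices the plan has not made.** True of r, the pooling and the time points. Both pooled and unpooled results are therefore shown, and the planned mixed model could do better (.94-.99 at 0.20 SD in the favourable case). A reader might infer that the trial is underpowered for its main question. At 0.27 SD power is at least .92 for the assumed r, so that inference fails.

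**The plan claims only that it can investigate moderators and mediators, and states no power for either.** Correct, but it gives the high main-effect power as the reason, and that reason does not hold for moderators. A 0.20 SD subgroup difference is admittedly large, being as big as the whole main effect in the sensitivity case; smaller differences have less power still. A reader might also infer that mediation is shown to be underpowered. Nothing here shows that.

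**Conclusion.** The point holds and the paragraph is wrong as written in two respects. First, an unconditional .999 is offered as power for a small effect. On the reading that best fits the text it applies to a net change of about 0.40 SD, and at 0.20 SD a two-time-point test has .69-.90 (three groups) or .78-.94 (pooled). Second, main-effect power is used to justify moderator and mediator analyses, while moderator power for a 0.20 SD difference is .28-.42, and .49-.63 even in the favourable case.

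These figures rest on 750 analysed, equal attrition, identical controls and r between .5 and .7; the moderator figures add two equal subgroups and pooled controls. Confidence is high on the moderator inference and on the ambiguity of f = .10. The exact main-effect figure stays conditional on settings only the sponsor can supply. The sample size and the design are not in question.

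**What to change.** Keep the sample size and the design, and revise the power paragraph in section 1.3.

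1. State the original G*Power settings (groups, measurements, correlation, effect-size option) and the net change in SD units that f = .10 represents under them. Do not enter 0.40 SD unless those settings confirm it. Quote the effect size taken from the source cited for f = .10.
2. Replace the unconditional .999 with power conditional on a net change in SD units and on r, for the test actually planned. Say whether controls are pooled and which time points enter, and state the attrition assumption. If the test is at two time points with 750 analysed, the figures for r = .5 to .7 are 69-90% (three groups) or 78-94% (pooled) at 0.20 SD, and 92-99% or 96-99.7% at 0.27 SD. If the mixed model is the main analysis, give its power under its own stated assumptions.
3. Bring the risk-table entry on small effects into line with these figures.
4. Replace the moderator and mediator sentence with a statement that both analyses are exploratory and that a null moderator result does not show equal effects. As illustration, add that power for a 0.20 SD difference between two equal subgroups is 28-42% for r = .5 to .7. Give no mediation figure unless one is computed.

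The cost is protocol wording and a less favourable stated figure. No extra participants are needed.

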Measurement: Wellbeing is the primary outcome of this study. Comprehensive work has recently been published with recommendations for standard wellbeing measurements in Norway[42]. We will use the recommended shortlist which includes 23 questions on different aspects of quality of life (e.g., life satisfaction, positive affect, meaning, social wellbeing, negative affect) and background variables. The shortlist has been included in the Public Health Surveys in the counties and several other studies, and data has been collected from more than 100,000 individuals in 2019/2020. In addition, we will use the Satisfaction With Life Scale (SWLS), one of the most common wellbeing instruments globally (measuring subjective wellbeing, including global life satisfaction, cognitive and affective evaluations of life) with excellent psychometric properties[43]. We will also use a brief 8-items Flourishing Scale suitable for a general population (measuring psychological wellbeing, including self-perceived success in important areas such as relationships, self-esteem, purpose, and optimism)[44]. In addition, we will use five questions from Pearlin and Schooler (1978) Mastery Scale which measure a general attitude of the possibility to influence once life situation[45]. Secondary outcome measures include mental ill-health. To measure symptoms of depression and anxiety we will use the Symptom Checklist-8 (SCL-8), a short-form version of the original

SCL-25 with solid psychometric properties[46]. These instruments are commonly used in similar studies, making the results comparable to existing research findings[36]. We also add two questions from The Short Form Survey-12 (SF-12) to have a measure for physical health. The average time to complete the questionnaire is 10 minutes. In addition to the questionnaire, we will measure the participants' compliance in incorporating each of the five actions into their daily life. This will be assessed via replies to the weekly SMS messages.

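### Wellbeing is primary only as a construct: no deciding scale, arm contrast, time or multiplicity rule is named, and the three-group interaction cannot show benefit over the active control

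*Combined protocol and SAP*

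**What the plan says.** All of this is in section 1.3 unless noted.

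- **Outcome.** The measurement paragraph says "Wellbeing is the primary outcome of this study". It then lists "the recommended shortlist which includes 23 questions on different aspects of quality of life", with no total or domain score defined. It continues "In addition, we will use the Satisfaction With Life Scale (SWLS), one of the most common wellbeing instruments globally" and "We will also use a brief 8-items Flourishing Scale suitable for a general population".
- **Mastery.** The main hypothesis is that 5WaysA "will improve wellbeing and mastery and hence provide the municipalities with an effective measure for mental health promotion". The mastery items are described before the secondary outcomes are introduced, so their status is unclear.
- **Arms.** There are 750 participants on intervention, 375 on active wait-list (weekly activity log) and 375 on passive wait-list. The reason for the second control is given: "We add the active control because we are aware of the limitations in passive wait-list control group conditions". The stated goal is: "The goal with this design is to demonstrate the initial efficacy and feasibility of the 10 week 5WaysA intervention".
- **Times.** Research question 2 asks "To what extent are the effects short-term and long-term (i.e., 10 weeks and 12 months". The power paragraph refers to the second measurement. Under procedures, M2 is the one-month booster for the intervention arm, but for the controls it is the point when the intervention arm has finished (about 10 weeks). Controls receive 5WaysA at five months. The schedule in section 3.2 has one between-group row and does not call it primary.
- **Analysis.** A two-way mixed ANOVA of wellbeing over time is planned, plus linear mixed models, without saying which decides. Two-tailed alpha .05 appears only in the power paragraph, for one group-by-time interaction.

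**The concern.** Two separate gaps follow.

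First, nothing says which instrument carries the main hypothesis. A favourable result on the shortlist, the SWLS or the Flourishing Scale could each be presented as confirming it, and the error rate of that claim is not fixed in advance.

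Second, the only test described for the three arms is a group-by-time interaction. With three groups this is a two-degree-of-freedom test that asks whether the mean changes differ somewhere. It can be significant because both 5WaysA and logging differ from passive waiting. The active control was added deliberately, yet no comparison with it is committed to. The trial could report a significant result and leave open whether 5WaysA does better than keeping a weekly log, which matters for a tool offered to municipalities as effective.

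**Working it through.** **1. The plan's own power figure.** Inputs from the power paragraph: N = 750 retained, f = .10, alpha = .05. Assumed, because not stated: two times and a correlation of .5 between them. The noncentrality is λ = N·f²·m/(1−ρ) = 750 × .01 × 2/.5 = 30. With three groups (df 2 and 747) power is .9992, and with two groups (df 1 and 748) .9998. The stated .999 therefore reproduces, and it fits a three-group interaction.

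**2. Set-up for the error rates.** The 750 retained are split 2:1:1, giving 375, 187.5 and 187.5 (equal attrition assumed). The variance of change is 1, which follows from r = .5 and unit variance at each time. The shortlist counts as one score. Let I, A and P be the mean changes for intervention, active and passive.

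- Interaction: Q = z₁² + z₂² > 5.99, with z₁ = (I − (A+P)/2)/√(1/375 + 1/375) and z₂ = (A − P)/√(2/187.5).
- Favourable: Q significant, and I above A or above P at two-sided .05, using standard error √(1/375 + 1/187.5) = .0894.
- Assumed decision rule: success on any one scale counts.

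**3. Results with no true effect (simulation).**

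| Scales tested | Correlation of changes | Favourable | Any direction |
|---|---|---|---|
| One named | – | 2.2% | 5% |
| Three, one time | .8 to .5 | 4.6-5.8% | 10-13% |
| Three, one time | 0 | 6.5% | 14.3% |
| Three, one time | .9 | 3.9% | 8.5% |
| Four (with mastery), one time | .8 to .5 | 5.4-7.2% | – |
| Three, two times | .8 to .5 (between times .7 to .5) | 7.6-10.4% | 16-22% |

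Check at zero correlation: 1 − .95³ = .143. The two-time row applies only to times before the controls receive 5WaysA, that is 10 weeks and five months (intervention M4, control M3).

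**4. What the interaction does not show.** Let 5WaysA and logging each add an assumed 0.20 SD, with passive control unchanged, on one scale. The interaction is then significant with 5WaysA above passive in 51% of trials. The true difference between 5WaysA and active is zero, so that contrast is significantly favourable in 2.5%.

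**5. Power if contrasts decide instead.** Assume logging has no effect and SD of change is 1. Against pooled controls the standard error is √(2/375) = .0730; at d = .20, z = 2.74 and power is .78. Against active control, .20/.0894 = 2.24 and power is .61. Joint power for (a) pooled controls, then active, and (b) superiority over both controls:

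| d | (a) | (b) |
|---|---|---|
| .20 | .58 | .42 |
| .30 | .92 | .85 |
| .40 | .99 | .99 |

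The last row is about the planned effect: for intervention against pooled controls of equal size, d² × 750/4 = 30 gives d = .40. The lower rows are relevant because section 1.1 cites effects of 0.2 to 0.3 for face-to-face interventions of this kind.

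**The case against.** The strongest reply is that the documents never say each scale will be tested separately, or that any one success would count. They speak of one comparison of wellbeing and one interaction. Silence is not a plan to select the best scale, and the promised preregistration could name the measure. The stated goal is also modest. This stands in part: the error rates in the table are conditional on an assumed rule and on correlations that the documents do not give. It does not remove the omission, because no section supplies any other rule, and the main hypothesis is aimed at a claim of effectiveness.

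A reader might go further than the documents allow in four ways.

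- **The power of .999 is wrong.** It is not. It reproduces for one interaction on one scale.
- **Naming a contrast alone is enough to reach 2.5%.** A single pre-named two-sided contrast has a 2.5% favourable rate only if the scale is named too. With one contrast and three scales the rate is 4.9-6.3% at correlations .8-.5. The like-for-like comparator for the interaction-gated rates is 2.2%.
- **Testing at 12 months inflates the error in the same way.** By then the controls have had 5WaysA, so there is no untreated randomised comparison. Section 3.2 lists the 12-month analyses by group, apart from the between-group row.
- **The 51% is a false-positive rate.** It is not. In that scenario 5WaysA truly beats passive control; the result is simply no evidence of benefit beyond logging.

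**Conclusion.** The concern holds as a gap in the decision rule. Wellbeing is primary only as a construct, and the plan names no deciding scale, score, contrast, time or multiplicity rule. The power paragraph's second measurement does not identify a common time across arms. If any of three scales could carry the claim, the favourable error rate at one time is roughly double that of one named scale: 4.6-5.8% against 2.2%, with 3.9-6.5% over correlations of change from .9 to 0. That inflation is modest and rests on the assumed rule.

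The contrast gap is the weightier part and does not depend on the number of scales: a significant three-group interaction does not establish benefit over the active control. The plan should be changed, but the documents do not show that a misleading analysis is intended. The preregistration and the timeline figure were not available.

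**What to change.** Before analysis, in the plan and the registration:

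1. Name one wellbeing scale and its score, at the sponsor's choice, as primary at 10 weeks (intervention M3 against control M2), before the controls receive 5WaysA.
2. Replace the interaction as the deciding test with pre-specified single-degree-of-freedom contrasts that include intervention against active control, with overall two-sided alpha of .05. Two workable forms are (a) pooled controls first, then active control only if the first succeeds; or (b) superiority over each control, with both required at two-sided .05.
3. Claim benefit beyond activity logging only if the active-control contrast succeeds.
4. Report the mean changes of all three groups with confidence intervals. Treat the other scales, mastery and later times as secondary.

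The cost is wording in the protocol, analysis plan and registration; no new data are needed. The downside is that one scale carries the confirmatory claim, and joint power is lower than the stated .999 if the true effect is small: .58 for (a) and .42 for (b) at d = .20, but .99 for both at about the planned effect.
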